#### Determination of Patients for Analysis:

All enrolled patients that received a BSC penile prosthesis with data available will be included.

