### 4 REGISTRY DESIGN SUMMARY

The PROPPER Registry is a post-market, multi-center, non-interventional, observational collection of clinical outcomes for patients implanted with a BSC penile prosthesis for the treatment of erectile dysfunction.

As an observational collection, the registry does not dictate patient selection for implantation of BSC devices, and does not direct physicians in the medical and surgical management of patients. Physicians are free to select and manage their patients according to their usual practice. Concomitant urological procedures are allowed and will be recorded. However, outcomes data on these procedures will not be collected, with the exception of select data for any concomitantly implanted AMS 800 Artificial Urinary Sphincters or AdVance slings for the treatment of incontinence.

BSC recommends that all devices are implanted according to the device specific Instruction for Use (IFU) and/or Operating Room (OR) manuals and the site or physician's standard of care.

Patient data will be collected from the baseline/pre-operative visit, the procedure, and follow up evaluations which will occur according to each physician's standard of care, up to 5 years post-operatively. A 1=year follow up evaluation will be required, and a 2-year follow-up evaluation will be strongly encouraged. Follow-up evaluations may occur during visits with the physician and/or by telephone or mail.

Each physician will determine if the device implantation procedure was successful based on his/her standard of care. Any reported intra-operative complications will be collected in the registry database. Success will be measured post-operatively by querying patients about device use.

The PROPPER Registry is designed to obtain post market safety and effectiveness information as well as to serve as an active surveillance system for collecting device related events or complications and malfunctions in patients implanted with BSC penile prostheses and reporting product complaints to BSC. This will provide a robust database of clinical information from which a number of analyses can be performed.

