### 6 PATIENT ENROLLMENT

All patients who meet eligibility criteria should be encouraged to enroll in the registry. Patients will be considered enrolled once they have signed an informed consent. If a site has a waiver of informed consent each patient from that site will be considered enrolled once the first data records are entered into the database. A unique patient identifier will be assigned to each patient at enrollment (upon signing an ICF or database entry). The PROPPER Registry is expected to enroll approximately 500 to 1500 patients at up to 16 sites throughout the US and Canada. Enrollment is expected to be over a one to two year period with up to five year patient follow-up. A total of more than 500 patients are anticipated to be implanted and entered into the registry database per year of enrollment. Based on historical estimates and assuming 10 to 15 participating physicians, the following number of each BSC penile prosthesis type will be implanted each year of enrollment: 500 AMS 700® Inflatable Penile Prostheses, 15 AMS Ambicor® Penile Prostheses, and 20Spectra™ Concealable Penile Prostheses.

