### 8.2 SAFETY OBJECTIVES

Safety will be assessed by collection and review of all reported intra-operative and postoperative device or surgery related clinical study events recorded during the implantation or any follow-up visits (for BSC products only).

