#### Endpoint:

- Complications (adverse device effects/events)
  - Intra-operative device or surgery related complications reported during Implantation visit (e.g., cylinder crossover)

- Post-operative device or surgery related complications reported during follow-up (e.g., mechanical malfunction, infection)
- Unanticipated and serious adverse device effects (per ISO 14155:2011)
- Deaths (related to the device or implantation procedure)
- Device Malfunctions
  - Device deficiencies or malfunctions (per ISO 14155:2011)
- Revision procedures related to the device or implantation procedure

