#### Statistical Analysis:

Descriptive statistics (number of events, number and proportion of patients) will be summarized by complication category by device type and for the full group. Kaplan-Meier method will be used to estimate the major complication event rate at 1 year postoperative follow up by device type and overall for all BSC penile prostheses recipients.

Descriptions will also be prepared of the following details associated with device related complications in each category, and will include the following as available for each:

- Treatment for complication
- Location of treatment
- Resolution (resolved or continuing)

Additional analyses may be prepared for other follow-up time such as 6 month, 2, 3, 4, and 5 years.

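### The recipients-only safety set leaves out of the intra-operative complication proportion any enrolled man whose implantation was stopped by a complication before a BSC device was placed

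*Combined protocol and SAP*

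**What the plan says.** **Enrolment.** Section 5.1 makes a man eligible when a BSC prosthesis is recommended to him. Under section 6, "Patients will be considered enrolled once they have signed an informed consent"; at sites with a consent waiver, "each patient from that site will be considered enrolled once the first data records are entered into the database". Neither event requires that a device be implanted.

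**Safety scope.** Section 8.2 opens: "Safety will be assessed by collection and review of all reported intra-operative and postoperative device or surgery related clinical study events". Its endpoint list includes intra-operative complications related to device or surgery, and deaths related to the device or the implantation procedure.

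**Summary.** Under Statistical Analysis in section 8.2, "Descriptive statistics (number of events, number and proportion of patients) will be summarized by complication category by device type and for the full group". The Kaplan-Meier estimate of major complications at 1 year is given "by device type and overall for all BSC penile prostheses recipients".

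**Analysis set.** Section 8.2 closes with: "All enrolled patients that received a BSC penile prosthesis with data available will be included". The same sentence closes each effectiveness objective in section 8.3. *Received* is not defined.

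**Procedure outcome.** Section 4 says: "Each physician will determine if the device implantation procedure was successful based on his/her standard of care".

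**The concern.** A recipients-only set suits satisfaction, device use or IIEF-5, which have no meaning without a device. It does not suit an endpoint that can occur before the device is placed. A complication that ends the operation at that stage is both the outcome of interest and the reason the man leaves the set, so exclusion depends on the outcome being measured.

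Safety is the first outcome named in the main objective (section 3.1). The intra-operative proportion would describe completed implantations only and would omit procedures that a complication brought to an end. Read literally, a procedure-related death before placement would also fall outside the set, although it is a listed endpoint.

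**Working it through.** **Step 1: follow one man through the text.** A prosthesis is recommended and he consents, so he is enrolled (sections 5.1 and 6). Surgery starts, a complication occurs, and the operation stops with no BSC device placed.

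- Is the event collected? Yes. The event form in section 7.4.1 covers events during surgical implantation as well as after it.
- Is it within the stated safety scope and endpoints? Yes. The opening of section 8.2 and its endpoint list do not require that a device was received.
- Is he in the set for the proportion? No. He did not receive a BSC prosthesis.
- Does another section restore him? No. The plan defines no started-procedure set and no listing of uncompleted implantations. The implantation data in the synopsis and section 8.5 include no item for an uncompleted procedure or an intended device.

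**Step 2: direction of the effect.** Let N be recipients, c the intra-operative complication proportion among them, B the stopped cases without a BSC device, and A those among B with a counted complication.

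- Plan's set: cN / N = c.
- All started: (cN + A) / (N + B).

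The second exceeds the first when A/B > c. If every stopped case had a complication, A = B and the plan's figure is too low whenever c < 1. Cases stopped for other reasons work slightly the other way: with 10 events in 500 recipients and one stop without a complication, 10/500 = 2.000% against 10/501 = 1.996%.

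**Step 3: effect of one case by device type.** The documents state no complication or stopping rate, so there is no planned figure to reproduce. Section 8.1 gives expected yearly implants of 500 AMS 700, 15 Ambicor and 20 Spectra, in total 535. These are men implanted, so a stopped case is additional to them. If no recipient has a complication and one procedure is stopped by one:

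| Group | Plan's set | All started |
|---|---|---|
| Spectra | 0/20 = 0% | 1/21 = 4.8% |
| Ambicor | 0/15 = 0% | 1/16 = 6.3% |
| AMS 700 | 0/500 = 0% | 1/501 = 0.2% |
| All | 0/535 = 0% | 1/536 = 0.2% |

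**Step 4: range for the full group, on assumed inputs.** Let a be the share of started procedures stopped by a complication before placement. The all-started proportion is c(1 − a) + a, so the understatement is a(1 − c), whatever the number of procedures. Both c (1% to 3%) and a (0.25% to 2%) are assumptions.

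| c (plan's set) | a = 0.25% | a = 1% | a = 2% |
|---|---|---|---|
| 1% | 1.25% | 1.99% | 2.98% |
| 2% | 2.245% | 2.98% | 3.96% |
| 3% | 3.24% | 3.97% | 4.94% |

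The understatement runs from 0.25 × 0.97 = 0.24 points to 2 × 0.99 = 1.98 points. The upper end is demanding. At c = 1% and a = 2%, 2/2.98 = 67% of all intra-operative complications would end the operation. At c = 3% and a = 0.25%, the share is 0.25/3.2425 = 8%.

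**The case against.** **Recipients are the declared population.** The synopsis and section 4 describe outcomes in men implanted with a BSC prosthesis, and the plan never promises a failed-implantation rate. This stands as a defence of the recipient set for post-operative outcomes, the Kaplan-Meier estimate and effectiveness. It does not cover endpoints that the plan itself ties to surgery or the procedure, whose natural denominator is procedures started.

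**The event is not lost.** It is recorded under section 7.4.1 and reviewed under the opening of section 8.2. If it is serious, unanticipated or fatal, it is reported to the sponsor under Table 5 in section 16.1. Section 8.5 also summarises all available implantation data. This stands. A reader might infer that such a man vanishes from the registry or that the plan conceals failed procedures; the documents do not support that. What he loses is his place in the analysed proportion.

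***Received* is undefined.** A device placed and removed in the same operation may count as received. This stands, and it narrows the point to men in whom no BSC device was placed.

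**Section 4 does not mention abandoned operations.** It leaves procedural success to the physician, and the same paragraph measures success post-operatively by device use. This also stands: the passage allows for an unsuccessful procedure and says nothing more. The point rests on the enrolment rule and the analysis-set sentence.

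**The analysis is descriptive.** It has no hypothesis, threshold or safety-based sample size, which limits the consequence for the full group. It helps less for the small device strata, because section 8.1 contemplates publishing on as few as 10 to 25 Spectra patients.

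**Conclusion.** The point holds for enrolled men whose BSC implantation was started and then stopped by a complication before a BSC device was placed. For them the analysis-set sentence in section 8.2 conflicts with that section's own scope and endpoints, and the omission can only lower the reported intra-operative proportion.

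The size is unknown. The full-group effect is probably small: 0.24 to 1.98 points across the assumed grid, with the upper end requiring most complications to end the operation. One case matters in the small strata, at 4.8% for Spectra and 6.3% for Ambicor on one year's expected implants, assuming no other complication there.

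A reader might infer that the reported rate could be half the true one. The documents do not support that. With a true rate of 2% and 1% of procedures stopped by a complication, the plan's set gives (2 − 1)/(100 − 1) = 1.01%, but this merely restates an assumption that half of all complications end the operation. The change is worth making because the rule selects on the outcome and is cheap to correct.

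**What to change.** In section 8.2, for intra-operative and procedure-related endpoints only, define the set as all enrolled patients in whom implantation of a BSC penile prosthesis was started (first incision), whether or not a device was in place at closure. Report the number of uncompleted implantations overall, and by intended device where recorded. Define *received*, saying whether it covers a device placed and removed in the same operation. Keep the recipient set for post-operative, Kaplan-Meier and effectiveness analyses.

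Add one item to the procedure form: BSC device in place at closure (Y/N), with the intended device.

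The cost is a wording change and that form item. Intended device may be unavailable for patients already entered, so the breakdown by intended device may be incomplete for them. The reported complication proportion may be slightly higher. Patient management is unaffected.

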#### 8.3 EFFECTIVENESS OBJECTIVES

Effectiveness of the BSC penile prostheses will be assessed in all patients with data available at the required 1-year ( $\pm$  4 months) post-operative follow-up, and any of the following additional follow-up time points with data available:

- 3 months (± 1 month)
- 6 months (± 1 month)
- 18 months (± 1 month)
- 2 years (± 4 months)
- 3 years (± 6 months)
- 4 years (± 6 months)
- 5 years(± 6 months)

### 8.3.1 EFFECTIVENESS OBJECTIVE 1 – DEVICE USE AND SATISFACTION

To assess post-implantation patient satisfaction with the device and use of the device.

#### Endpoint:

- How satisfied are you with the device(s)? (5-point scale)
  - 1 Very Dissatisfied
  - 2 Dissatisfied
  - 3 Equally Satisfied and Dissatisfied
  - 4 Satisfied
  - 5 Very Satisfied
- Are you using the device? (Y/N)
  - (If yes) How often are you using the device? (less than once per month, or more than once per month)
  - How many times per month?
  - If no, why aren't you using the device? (Loss of partner, partner disinterest, device problem, device dissatisfaction, health decline, other, other device use reason)
  - If yes, and not using the device as often as desired, or if dissatisfied with the device, indicate why (Loss of partner, partner disinterest, device problem, device dissatisfaction, health decline, other, other device use reason)

#### Statistical Analysis:

The number and percentage of patients with responses in each category for the satisfaction and the device use questions at 1-year visit and any of the additional followup time points with data available will be summarized for each device type and overall for all BSC penile prostheses recipients.

#### Determination of Patients for Analysis:

All enrolled patients that received a BSC penile prosthesis with data available will be included.

#### 8.3.2 EFFECTIVENESS OBJECTIVE 2 – IIEF-5/SHIM QUESTIONNAIRES

To assess sexual function in IIEF-5 scores.

#### Endpoint:

The endpoint is the change in IIEF-5 total scores from baseline to 1-year post-operative follow-up.

#### Statistical Analysis:

The IIEF-5 total scores will be computed for each patient at baseline and 1-year follow up, and the change from baseline to 1-year follow up will be calculated. Descriptive summary statistics including mean, median, standard deviation (SD), and range will be generated by each device type and overall for all BSC penile prostheses recipients. For within patient change at 1-year follow up compared to baseline, signed rank sum test or paired t-test may be used when applicable.

Additional analyses may also be used to summarize the values at the other follow-up time points with data available along with changes from baseline for each device type and overall for all BSC penile prostheses recipients. Mixed effects model may be used to estimate the change from baseline across follow up visits when appropriate.

In addition, the number and percentage of patients with IIEF-5 scores meeting the following criteria will be calculated at baseline and at each post-treatment time point for each device type and overall:

- $\circ \leq 7$  points (severe ED)
- 8 to 11 points (moderate ED)
- 12 to16 points (mild-moderate ED)
- 17 to 21 points (mild ED)
- $\circ$  ≥ 22 points (no ED)

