Penile Measurements	0	0	0	0
Incontinence Data	0	0	0	0
Patient Questionnaires	SE	SE	SE	SE
Clinical Study Events/Complications	R†	R†	R†	R†

\* The same assessments, evaluations, questionnaires that were completed at baseline should be completed at follow-up

[figure not shown]
R = Required, O = Optional, SE = Strongly Encouraged, N/A = Not Applicable.

 $\dagger = if applicable$ 

- Demographics and Characteristics age, race/ethnicity, concomitant medical conditions and medications
- ED History primary etiology of ED, previous ED treatments (optional)
- Depression History query for any treatment of depression in past year optional at baseline and at annual follow-up
- Implantation Procedure Details surgical procedure details and implant model information, patient status post-op
- Device Use and Satisfaction query for device use and device satisfaction
- Penile Measurements pre-op flaccid and stretched length and girth, intra-op inflated penile length and girth and deflated stretched length, and post-operative inflated length and girth measurements, by physician
- Incontinence Data Daily pad use, pad weight tests, urodynamics, post-void residual (PVR) volume maximum flow rate

- Patient Questionnaires IIEF-5/SHIM erectile function questionnaire; EHS erection hardness question; SF-12 health-related quality of life questionnaire; AUA-SI symptom questionnaire; UCLA-PCI urinary, sexual and bowel function and bother questionnaire
- Clinical study events device or procedure related complications (adverse device effects/events), device malfunctions, revision procedures related to the device or implantation procedure

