### 7 DATA COLLECTION

Data will be collected via internet-based electronic data capture (EDC) with paper based questionnaires for collection of patient-reported outcomes (PRO) data. The PRO data will be entered into the registry database by the physician, physician staff or BSC staff. The EDC module will be developed and maintained by BSC.

Physicians are not required to complete all data fields in the database. Each will be asked to enter the required data at baseline/procedure and one-year follow-up for each

patient and optional data based on the information that they collect per their own standard of care.

Additional outcomes will be collected at whatever time frames are deemed appropriate by the physician, based on their standard of care for treatment of ED.

This is an observational collection of prospective patient data, with the following data required for each enrolled physician and patient:

- basic practice information for each physician
- baseline/pre-operative patient information: age, race/ethnicity, primary etiology of ED, relevant concomitant medical conditions and concomitant medications that might impact ED
- implantation surgery data: date of procedure, surgical approach, implant model type, drain, dressing, concurrent procedures, significant corporal fibrosis or scarring noted, curvature correction procedure(s) (e.g., for Peyronie's disease), and patient status post-op
- 1-year post-operative follow-up (at a minimum): each patient is asked 3 standardized questions during a visit or by phone to record any potential device related complications and their outcomes, patient satisfaction with implanted device(s) and use of device.

Refer to Table 1 for the study data collection schedule.

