### 7.3 PATIENT QUESTIONNAIRES

Patient questionnaires to measure effectiveness will be optional at baseline and at all follow-ups. The following validated, patient-reported outcome questionnaires are *strongly recommended* for all patients at baseline and follow-up:

- IIEF-5/SHIM erectile function questionnaire
- EHS erection hardness questionnaire
- SF-12 health-related quality of life (HRQOL) questionnaire

The following validated, patient-reported outcome questionnaires are recommended for all patients with post-prostatectomy ED or incontinence:

- AUA-SI/IPSS urinary symptom questionnaires
- UCLA-PCI urinary, sexual and bowel function and bother questionnaire

The questions for each individual questionnaire are provided in the Appendix.

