## **APPENDIX 1 - QUESTIONNAIRES**

# International Index of Erectile Function-5 / Sexual Health Inventory for Men (IIEF-5/SHIM)

The 5 specific questions comprising the IIEF-5/SHIM are shown below. Each question is preceded by the phrase, "Over the past 6 months,":

- 1. How do you rate your confidence that you could get and keep an erection?
  - 1 Very low
  - 2 Low
  - 3 Moderate
  - 4 High
  - 5 Very high
- 2. When you had erections with sexual stimulation, how often were your erections hard enough for penetration?
  - 1 Almost never/never
  - 2 A few times (much less than half the time)
  - 3 Sometimes (about half the time)
  - 4 Most times (much more than half the time)
  - 5 Almost always/always

3. During sexual intercourse, how often were you able to maintain your erection after you had penetrated (entered) your partner?

- 1 Almost never/never
- 2 A few times (much less than half the time)
- 3 Sometimes (about half the time)
- 4 Most times (much more than half the time)
- 5 Almost always/always

4. During sexual intercourse, how difficult was it to maintain your erection to completion of intercourse?

- 1 Extremely difficult
- 2 Very difficult
- 3 Difficult
- 4 Slightly difficult
- 5 Not difficult
- 5. When you attempted sexual intercourse, how often was it satisfactory for you?
  - 1 Almost never/never
  - 2 A few times (much less than half the time)
  - 3 Sometimes (about half the time)
  - 4 Most times (much more than half the time)
  - 5 Almost always/always

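### Section 8.3.2 would report 3-month IIEF-5 scores as post-treatment severity, although 33% to 67% of the questionnaire's stated 6-month recall period falls before the implant

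*Combined protocol and SAP*

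**What the plan says.** All references are to the combined protocol and SAP.

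- **Recall period.** Appendix 1 states that each of the five IIEF-5 questions is introduced by "Over the past 6 months".
- **Time points.** Section 8.3 assesses effectiveness at the required 1-year follow-up and at "any of the following additional follow-up time points with data available". That list includes 3 months and 6 months, each with a window of plus or minus 1 month.
- **Severity table.** Section 8.3.2 commits to the five severity categories without qualification: "the number and percentage of patients with IIEF-5 scores meeting the following criteria will be calculated at baseline and at each post-treatment time point". The patient set for this objective is every implanted patient with data, with no exclusion of early records.
- **Other uses of early records.** The same section allows, but does not require, summaries of change at the other time points and a mixed effects model across visits.
- **Endpoint.** The named IIEF-5 endpoint is the change from baseline to 1 year.
- **Whether early records arise.** Section 7 says "Additional outcomes will be collected at whatever time frames are deemed appropriate by the physician", and Section 7.3 says "Patient questionnaires to measure effectiveness will be optional at baseline and at all follow-ups". Table 1 nevertheless marks questionnaires as strongly encouraged at interim follow-up. The footnote attached to that column says "The same assessments, evaluations, questionnaires that were completed at baseline should be completed at follow-up".

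Nothing in the document shortens the recall period, ties it to the time since surgery, or sets early records apart.

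**The concern.** A score labelled as post-treatment should describe the period after treatment. When the recall period is longer than the time since implant, the patient is asked to rate a mixture of the period before surgery and the period after it. In the 3-month window this applies to every record.

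If men improve after implantation and answer for the period stated, the early severity table shows more severe dysfunction than men have after surgery. Part of any apparent improvement between 3 months and later visits would then come from pre-implant time dropping out of the recall period, not from a change in function. A mixed model fitted across visits would carry the same artefact into its estimated time course. A reader of a by-visit table would have no means of seeing this.

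The problem is specific to this instrument. In Appendix 1 the timed items of the SF-12 and UCLA-PCI look back 4 weeks and the AUA-SI one month. Section 7.3.2 ties the EHS to the most recent encounters. None of the timed recall periods reaches back before surgery at 2 months or later.

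**Working it through.** The document gives no figure for recall overlap, so there is nothing of its own to reproduce first.

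**Inputs**

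- Recall period: 6 months (Appendix 1, IIEF-5/SHIM).
- Analysis windows: Section 8.3.
- *m*: months from implant to completion of the questionnaire.

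**Formula**

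Pre-implant share of the stated recall period = max(0, 6 − *m*) / 6.

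**By month**

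| *m* (months) | Calculation | Share before implant |
|---|---|---|
| 2 | 4/6 | 67% |
| 3 | 3/6 | 50% |
| 4 | 2/6 | 33% |
| 5 | 1/6 | 17% |
| 6 or more | 0/6 | 0% |

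**By analysis window**

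| Time point | Window (months) | Records with pre-implant recall |
|---|---|---|
| 3 months | 2 to 4 | all |
| 6 months | 5 to 7 | those at 5 to under 6 (half the window's width) |
| 1 year | 8 to 16 | none |
| 18 months | 17 to 19 | none |
| 2 years | 20 to 28 | none |
| 3 years | 30 to 42 | none |
| 4 years | 42 to 54 | none |
| 5 years | 54 to 66 | none |

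Of the 8 time points, 1 is affected for every record, 1 is affected in the lower half of its window, and 6 are not affected.

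**What the arithmetic does not give**

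The percentages are shares of calendar time. Turning them into points on the 5-to-25 scale would need two things the document does not supply: how men weight the pre-implant period when they answer, and what their function was then. The second also varies by patient, because the registry includes revision, salvage and replacement implants as well as first implants.

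**The case against.** There are four points on the other side.

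1. **Calendar share may be a poor guide to the weight of the pre-implant period.** The first IIEF-5 item asks for a present rating of confidence. The other four depend on events: erections, intercourse or attempts at it. Under that wording the weight follows when those events happened, so the pre-implant weight could be well below or well above the calendar share. This stands. It adds to the uncertainty about size, but it does not make the recall period match the label.

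2. **The affected records may be few.** Only the 1-year follow-up is required, questionnaires are optional, and the physician sets interim timing. The Table 1 footnote says which instruments to repeat, not that a contact will take place at 2 to 4 months. This also stands, so the number of such records is unknown. They are plausible all the same: Table 1 strongly encourages questionnaires at interim follow-up, and Section 8.3 defines a window to receive them.

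3. **Nothing confirmatory is touched.** The IIEF-5 endpoint and its within-patient test are at 1 year. The other change summaries and the mixed model are discretionary, so an analyst could already leave early records out. Section 8.1 also says that at least 1 year of follow-up is generally wanted for the established devices, and it accepts 6 to 12 months for the newer ones. All of this is correct and is why the point is minor. The severity table, however, is stated as a commitment and leaves no such discretion.

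4. **Any dilution would be conservative, so a footnote would do.** If men improve, the 3-month table understates early benefit, and a note on recall would warn the reader. A footnote is better than nothing. It would still leave mixed-recall scores beside clean ones in the same by-visit table, and in any model that uses them.

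**Conclusion.** The concern holds and is minor. Followed as written, Section 8.3.2 would present as post-treatment severity any 3-month IIEF-5 scores whose stated recall period is one-third to two-thirds pre-implant. Records at 5 to under 6 months carry up to 17%.

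The calendar arithmetic is certain. The effect on the tables rests on three assumptions: early IIEF-5 records are collected, men answer for the period stated, and function differs before and after implant. The size of any score bias cannot be derived from the documents, and for revision or replacement implants even the starting state is unknown.

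The 1-year endpoint and its test are unaffected, as are all later time points.

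**What to change.** In Section 8.3.2, limit the post-treatment IIEF-5 severity tables, the change summaries and any mixed model to records completed at least 6 months after implant. Show earlier records (the 3-month window, and those at 5 to under 6 months) in a separate table or listing, labelled as having a recall period that includes time before the implant.

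If dropping the 5-to-under-6-month records from the 6-month summary seems too strict, keep them there and repeat the summary without them as a sensitivity analysis.

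Where the EHS was collected at 3 months, it can describe early erection hardness under the analysis already planned in Section 8.3.3.

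The cost is one or two sentences of SAP wording. No data are discarded, and no visit or questionnaire changes. The price is that there is no unqualified 3-month IIEF-5 result and, under the first option, fewer records in the 6-month summary. The EHS is only a partial substitute: it is a single hardness item, and Section 7.3.2 allows it to be collected just once per year.
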